11.1.3 Serious Adverse Events and Unexpected Adverse Device Effects

A Serious Adverse Event (SAE) is any AE that results in any of the following:

- Death
- Life-threatening injury or illness any AE that places the subject, in the view of the reporter, at immediate risk of death from the AE as it occurred (It does not include an AE that, had it occurred in a more severe form, might have caused death)
- Inpatient hospitalization or prolongation of existing hospitalization. However, preplanned or elective
 hospitalizations for pre-existing conditions that have not worsened during the course of the study
 should not be considered SAEs
- Persistent or significant disability/incapacity any AE that results in a substantial disruption of the subject's ability to conduct normal life functions
- Important medical events that may jeopardize the subject and may require medical or surgical intervention to prevent one of the outcomes listed above

An Unexpected Adverse Device Effect (UADE) is any device-related AE that meets one or more of the following criteria:

- Is not identified in nature, severity or frequency in current literature on the product
- Is life threatening, even if temporary in nature
- Results in permanent impairment of a body function or permanent damage to a body structure
- Necessitates medical or surgical intervention to preclude permanent impairment of a body function or permanent damage to a body structure

Also considered an UADE is any device malfunction that would be likely to cause or contribute to a death or serious injury if the malfunction were to recur.

11.1.4 Severity

Definitions for classification of severity appear below. For events reported on the AE eCRF, the Investigator will determine the severity classification based on these definitions, his/her clinical experience in the use of dermal fillers, and/or the subject's description of the event. [Note: A "severe" AE is not the same as a "serious adverse event," which is defined above.]

- Mild: Symptoms are barely noticeable or do not make the subject uncomfortable. The AE does not influence performance or functioning. Prescription drugs are not ordinarily needed for relief of symptom(s).
- Moderate: Symptoms are of sufficient severity to make the subject uncomfortable. Performance of daily activities is influenced. Tx of symptom(s) with prescription drugs or therapies may be needed.
- Severe: Symptoms are of sufficient severity to cause the subject severe discomfort. Performance of daily activities is compromised. Tx for symptom(s) with prescription drugs or therapies may be needed.

11.1.5 Relationship to Study Device

The Investigator will determine relatedness of the subject's symptom or problem to the study device or the injection procedure.

11.2 Procedures for Reporting Adverse Events

All AEs should be recorded through the AE eCRF.

11.3 Procedures for Unmasking of Study Devices

Not applicable. This is an open-label study.

11.4 Pregnancy

A female is considered a Woman of Childbearing Potential (WOCBP) unless she is postmenopausal for at least 12 months prior to study treatment administration, without a uterus and/or both ovaries, or has been surgically sterile for at least 6 months prior to study treatment administration.

In order to participate in the study, sexually active WOCBP must use one of the following reliable methods of contraception: hormonal methods or intrauterine device in use ≥ 90 days prior to study treatment administration, barrier methods plus spermicide in use ≥ 14 days prior to study treatment administration, or vasectomized partner. Non-sexually active WOCBP will not be required to practice a reliable method of contraception. These subjects may be enrolled at the Investigator's discretion if they are counseled to remain sexually inactive during the study and understand the possible risks in getting pregnant during the study.

12. Statistics

12.1 Sample Size Justification

Approximately 45 subjects will be enrolled. This is a pilot study and a formal sample size justification is not provided for this study. It is the opinion of the Sponsor that a total of 45 subjects will be sufficient to achieve the objectives of the study.

12.2 Efficacy Parameter Analysis

Statistical analyses will be conducted on an intent-to-treat (ITT) basis (i.e., all enrolled subjects that have fully passed screening and have received initial microneedling treatment will be included in the analyses). Descriptive statistics (i.e., mean, standard deviation, etc.) will be provided for all continuous variables and frequencies for all categorical variables collected in this study. When appropriate, exploratory inferential statistical analyses will be conducted using SAS® software (9.3 or higher). Comparisons between treatment groups will be performed using parametric or non-parametric testing, as appropriate. The level of significance will be fixed at 0.05. No adjustments for multiplicity will be performed.

Summary tables will be used to present population characteristics at Baseline. Data from the study questionnaires will be included. For categorical parameters, the number and percentage of subjects in each category will be presented. The denominator for percentage will be based on the number of subjects appropriate for the purpose of analysis. For continuous parameters, descriptive statistics will include n (number of subjects), mean, standard deviation, median, and range. No imputation will be used to account for missing data. No particular processing for outliers will be performed. Data will be presented as reported in the eCRF.

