10.1 Assessment Schedule

								Pe	riod II	
Period I			Track A Bellafill			Track B No-Tx				
	Visit	Screening	1	2	3	4	5a	6a	7a	5b
	1 week = 7D 1 month = 28D	W -4	D0	W3 ±3D	W6 ±3D	W12 ±1W	M1 ±1W	M3 [†] ±1W	M6 [†] ±1W	M3 ^{††} ±1W
Inf	ormed Consent	Х								
Inc	l/Excl Criteria, Med Hx	Х	X confirm							
UF	PT (if applicable)	Х	X ¹			X ¹	X ¹			
Fa	cial Scar Photography	Х				X ¹			Х	Х
Ве	llafill Skin Test	X Placement	X Reading							
Microneedling Treatment			Х	Χ	Х					
Ra	ndomization					R				
Bellafill Injections Initial injection Touch-up						l²	T ³			
ş	ASAS (Investigator)	Х						Χ	Х	Χ
nen	PGAIS (Investigator)					X ¹		Х	Х	Х
PGAIS (Investigator) SGAIS (subject) QoL Scar Impact Scale						X ¹		Χ	X	Χ
Ass	QoL Scar Impact Scale (subject)		X ¹						Х	Х
Со	n Meds/Procedures	X	Χ	Χ	Χ	Х	Χ	Χ	Х	Χ
Ad	verse Events	Х	Х	Χ	Χ	Χ	Χ	Χ	Χ	Х

[†] Visits to occur 3M and 6M after last injection of Bellafill (i.e., initial treatment or touch-up treatment)

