10.2 Study Period I

10.2.1 Screening Visit (W -4)

The following activities will be conducted:

- Informed Consent/HIPAA
- Subject Demographics/Medical History and Inclusion/Exclusion Criteria
- UPT (if applicable)
- Concomitant Medication/Procedures
- Facial Scar Photography
- Bellafill skin test and record the location of placement for review at the next visit
 - If applicable, collect any AEs, if any observed immediately after skin testing.
- ASAS
 - Performed by the Investigator.
- AE Assessment

^{††} Visit to occur 24W after Visit 1 (i.e., approx. 3M after Visit 4)

¹ Assessments to be performed prior to study treatment (if applicable)

² If randomized to Bellafill treatment

³ Bellafill touch-up injections administered as necessary

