10.2.4 Visit 4 (W12 ± 1W)

The following activities will be conducted:

- Concomitant Medication/Procedures and AE assessment
- UPT (if applicable)
- PGAIS
 - The Investigator will refer to Baseline photographs for PGAIS evaluation.
- SGAIS
 - The subject will refer to Baseline photographs for SGAIS evaluation.
- Facial Scar Photography
- Randomization
 - Subject allocated to Track A (Bellafill Treatment) or Track B (No Treatment) as per Section 7.4.
- Bellafill injections Subjects randomized to Track A only
 - Document the number of scars treated as well as the method and volume of treatment.
- Scheduling of next clinic visit
 - Track A: Subjects randomized to Bellafill Treatment attend Visit 5a at 1 Month from this visit.
 - Track B: Subjects randomized to **No Treatment** attend Visit 5b at 24 Weeks from Visit 1 (i.e., approximately 3 Months from this Visit 4).

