Appendix 1: Study Assessments

Appendix 2: Microneedling Procedure

Appendix 3: Skin Test Instructions for Use

Appendix 4: Bellafill Instructions for Use

APPENDIX 1: Study Assessments

A. Acne Scar Assessment Scale (ASAS): The ASAS is a static assessment scale that allows the Investigator to measure his/her impression of acne scar severity within the treatment area. The treatment area on each side of the face will be assessed separately, then will be averaged to obtain a global score.

Term	Grade	Description
Clear	1	No depressions are seen in the treatment area. Macular discoloration may be seen.
Very Mild	2	A single depression is easily noticeable with direct lighting (deep). Most or all of the depressions seen are only readily apparent with tangential lighting (shallow).
Mild	3	A few to several, but less than half of all the depressions are easily noticeable with direct lighting (deep). Most of the depressions seen are only readily apparent with tangential lighting (shallow).
Moderate	4	More than half of the depressions are apparent with direct lighting (deep).
Severe	5	All or almost all the lesions can be seen with direct lighting (deep).

B. Physician Global Aesthetic Improvement Scale (PGAIS): The Investigator will refer to baseline photographs and assess global overall improvement (but without considering untreated scars) as per the following:

Rating	Description
5 = Much improved	Marked improvement in appearance from the initial condition, touch-up treatment(s) is not indicted
4 = Improved	Obvious improvement in appearance from the initial condition, but a touch-up or re-treatment is indicated
3 = No change	The appearance is essentially the same as the original condition
2 = Worse	The appearance is worse than the original condition
1 = Much Worse	The appearance is much worse than the original condition

C. Subject Global Aesthetic Improvement Scale (SGAIS): The degree of aesthetic improvement will be assessed by the subject using the SGAIS as defined below. The subject will refer to baseline photographs and assess global overall improvement (but without considering untreated scars) as per the following:

Rating	Description
5 = Much improved	Marked improvement in appearance from the initial condition
4 = Improved	Obvious improvement in appearance from the initial condition
3 = No change	The appearance is essentially the same as the original condition
2 = Worse	The appearance is worse than the original condition

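### Section 12.2 names no baseline adjustment for the Track A v Track B comparison, although Screening ASAS is already collected and could narrow the interval at almost no cost

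*Combined protocol and SAP*

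**What the plan says.** Section 12.2 states the between-track method as "Comparisons between treatment groups will be performed using parametric or non-parametric testing, as appropriate". It adds that, when appropriate, "exploratory inferential statistical analyses will be conducted", at a fixed 0.05 level without multiplicity adjustment. No model, covariate or change-from-baseline analysis is named; baseline enters only through summary tables of population characteristics. Section 12.1 plans about 45 subjects and gives no effect size, SD or power.

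ASAS is rated at Screening (10.2.1: "Performed by the Investigator") and then at Visits 6a, 7a and 5b (10.3.2, 10.3.3, 10.4.1); the table in 10.1 agrees. Appendix 1 makes it a numeric score: "The treatment area on each side of the face will be assessed separately, then will be averaged to obtain a global score". Section 8 calls ASAS validated and does not say this of the other scales.

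At Visit 4, where 1:1 randomisation takes place (7.4, 10.2.4), the ratings are PGAIS and SGAIS. Both judge change against earlier pictures; for PGAIS, "The Investigator will refer to Baseline photographs for PGAIS evaluation". ASAS is not listed there.

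**The concern.** Track B has a single Period II visit, 5b, so Visit 6a v Visit 5b is the only ASAS comparison between tracks at roughly the same time. With about 22 per track it will be imprecise. Entry is by scar count (at least four scars) with no ASAS limit, so subjects may differ in severity at the start. A starting severity that predicts the outcome would otherwise stay in the error term, and chance imbalance between small groups would pass into the estimate.

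What is at stake is interval width, and having one analysis fixed beforehand instead of a choice of tests made once data are in hand.

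**Working it through.** The plan gives no precision figure, so there is none of its own to reproduce.

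**Inputs**
- N = 45 (12.1), allocated 1:1 (7.4), taken as 22 v 23.
- Two-sided 5% level (12.2 gives 0.05; two-sided is assumed).
- Outcome SD set to 1, so results are in SD units (assumed).
- Correlation ρ between Screening ASAS and Month 3 ASAS: not in the documents; 0, 0.3 and 0.5 are used.

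**Unadjusted comparison**
- Half-width = t(0.975, 43) × √(1/22 + 1/23) = 2.0167 × 0.2982 = **0.601 SD**.

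**ANCOVA on Screening ASAS**
- Half-width = t(0.975, 42) × √[(1 − ρ²)(1/22 + 1/23)] × √(42/41).
- The last factor, √[(N − 3)/(N − 3 − k)] with k = 1 covariate, allows for chance imbalance in the covariate.
- The part without ρ is 2.0181 × 0.2982 × 1.0121 = 0.609.

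| Assumed ρ | √(1 − ρ²) | Half-width (SD) | Against 0.601 |
|---|---|---|---|
| 0 | 1.000 | 0.609 | about 1% wider |
| 0.3 | 0.954 | 0.581 | about 3% narrower |
| 0.5 | 0.866 | 0.528 | about 12% narrower |

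Break-even is where 0.609 × √(1 − ρ²) = 0.601, that is ρ = √[1 − (0.601/0.609)²], about 0.16. Below that, adjustment costs slightly more than it returns.

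**Fewer randomised.** Section 7.2 counts a subject as enrolled at consent, so fewer than 45 may reach Visit 4. The same formulas at ρ = 0.3 give 0.640 to 0.620 SD with 40 randomised and 0.677 to 0.657 SD with 36.

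**Change from Screening is not an equivalent fix.** With equal SDs its variance is 2(1 − ρ) times that of the raw outcome: 1.4 times at ρ = 0.3 and 1.0 at ρ = 0.5. It is worse than no adjustment whenever ρ is below 0.5.

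**Timing of the comparison.** Section 10.1 puts Visit 6a three months after the last Bellafill injection; 10.3.2 puts it three months from Visit 4. A month is 28 days in 10.1. For a subject touched up at Month 1, the first reading places 6a at 4 + 12 = 16 weeks after Visit 4. Visit 5b, at 24 weeks from Visit 1, falls about 24 − 12 = 12 weeks after Visit 4. The two visits match for touched-up subjects only under 10.3.2.

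**The case against.** The strongest reply is that 12.2 is silent, not wrong. Its wording permits ANCOVA, Screening ASAS will be in the database, and nothing is lost unless the analyst leaves it out. This is also a pilot with exploratory inference and no named primary endpoint in Section 12, so choosing ASAS at Month 3 is a judgement. All of that stands, and it keeps the point small. What remains is that the plan names no adjusted model, and naming one now is almost free.

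Two stronger readings are tempting.

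A reader might infer that the comparison is biased or invalid. The documents do not support this: allocation is random and 1:1, so omitting a covariate affects precision and chance imbalance, not expectation.

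A reader might also infer that the missing Visit 4 ASAS is a second, sizeable loss, because the latest pre-randomisation ASAS is about 16 weeks old (Week −4 to Week 12) and precedes all three microneedling sessions. The absence is real, but its cost cannot be established:
- The gain depends on three undocumented correlations: Screening with outcome, Visit 4 with outcome, and the two ratings with each other. Over a set of assumed values the squared half-width falls by between 0.7% (0.25/0.3/0.7: 0.590 to 0.588 SD) and 30% (0.5/0.7/0.7: 0.528 to 0.441 SD). At 0.5/0.4/0.8, R² = (0.25 + 0.16 − 0.32)/0.36 = 0.25, the same as Screening alone, and the half-width rises from 0.528 to 0.534 SD.
- Visit 4 PGAIS and SGAIS, rated before treatment, partly stand in for it, since Screening severity plus rated change says something about current severity. Suppose PGAIS correlates 0.7 with Visit 4 ASAS given Screening and adds nothing beyond it. At 0.3/0.5/0.6, Screening plus PGAIS gives 0.563 SD, against 0.581 for Screening alone and 0.534 with Visit 4 ASAS.
- In this open-label study the Investigator or a delegate consults a site list of randomisation numbers (7.4). If upcoming assignments are visible, a Visit 4 rating could be made with the allocation known, and adjusting for it could then introduce bias. Screening ASAS is far less exposed.

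**Conclusion.** The concern holds as a minor analysis choice. Section 12.2 leaves unused, as written, a baseline value that the protocol already collects. At assumed correlations of 0.3 to 0.5, ANCOVA on Screening ASAS takes the half-width from 0.601 SD to between 0.581 and 0.528 SD; if the covariate is uninformative it rises to about 0.609 SD. These figures rest on all 45 being randomised and rated, and on treating the averaged ASAS grade as numeric. Validity is not in question. The lack of ASAS at Visit 4 is a fact of the schedule, but it supports only an optional suggestion.

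**What to change.** 1. In 12.2, name one exploratory model: Track A v Track B on ASAS at the Month 3 visit (6a v 5b), ANCOVA with Screening ASAS as covariate, reporting the adjusted difference with its 95% CI. Cost: one sentence, no new data, one degree of freedom.
2. Before that comparison is used, reconcile 10.1 with 10.3.2 on whether Visit 6a is timed from the last injection or from Visit 4. Cost: consistent wording in the sections that give the visit timing.
3. Optional: consider an ASAS rating at Visit 4, made before the allocation can be known, and state in 12.2 whether it enters the model. Cost: one two-sided rating per subject at an existing visit, wording in 10.1 and 10.2.4, and a second degree of freedom, with no assured gain.

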12.3 Safety Analysis

Safety analyses will be performed in terms of incidence and severity of adverse events. These will be tabulated and a complete listing of all reports of adverse and/or unexpected events will be presented.

Concomitant medications will be coded to generic terms. The listing will include study treatment date, start and stop date, and whether the drug was taken during study treatment.

13. Administrative Issues

This protocol will be conducted in accordance with the applicable U.S. Food and Drug Administration (FDA) regulations and guidelines and ICH-GCP Guidelines.

13.1 Protection of Human Subjects

13.1.1 Compliance with Informed Consent Regulations (21 CFR Part 50)

Written informed consent will be obtained from each subject prior to enrollment into the study (i.e., before performing any screening evaluations or procedures).

13.1.2 Compliance with Institutional Review Board Regulations (21 CFR Part 56)

This study will be conducted in accordance with IRB regulations (U.S. 21 CFR Part 56.103). The Investigator must obtain approval from a properly constituted IRB prior to initiating the study and obtain re-approval at least annually.

13.1.3 Compliance with the ICH-GCP Guidelines (ICH E6)

This protocol will be conducted in accordance with the applicable ICH-GCP Guidelines (ICH E6).

13.2 Changes to the Protocol

Strict adherence to the protocol is necessary to assure validity of the study. The Investigator must notify the Sponsor or designee and the reviewing IRB of significant deviations from this protocol. Significant deviations to the protocol will be documented and maintained as part of the study record. Lost to follow-up, out of window visits or assessments missed due to the subject's non-participation will be documented, but not considered significant deviations.

The Investigator must not implement any changes to the protocol without approval by the Sponsor and prior review and documented approval from the IRB, except where necessary to eliminate immediate hazards to study subjects, or when the changes involve only logistical or administrative aspects of the study (e.g., change of telephone numbers).

No amendments to the protocol will be implemented without the prior written consent of the Sponsor. Should an amendment be necessary, the reviewing IRB and FDA may require review and approval of it prior to implementation.

13.3 Subject Confidentiality and Privacy

A report of the results of this study may be published or sent to the appropriate health authorities in any country in which the study device may ultimately be marketed, but the subject's name will not be disclosed in these documents. The subject's name may be disclosed to the Sponsor of the study (Suneva), the CRO (ethica CRO Inc.), the governing health authorities (e.g., FDA) if they inspect the study records. Appropriate precautions will be taken to maintain confidentiality of medical records and personal information.

Written authorization will be obtained from each subject prior to enrollment into the study in accordance with the applicable privacy requirements (e.g., the Health Insurance Portability and Accountability Act Standards for Privacy of Individually Identifiable Health Information - HIPAA).

13.4 Required Regulatory Documents

It is the responsibility of the Investigator and study staff to maintain a comprehensive and centralized filing system of all study-related documentation, which is suitable for inspection at any time by the study monitor, the IRB, and the FDA. Elements should include:

- Subject files containing the completed case report forms, supporting source documentation and the informed consent, with signatures by the Investigator or sub-Investigators.
- Pharmacy or Investigator files, containing the investigational agent accountability records or dispensation logs and all study agent related correspondence.
- Confidential disclosure agreement with the Sponsor.
- Financial disclosure forms for each Investigator or sub-Investigator.
- Study files, containing the following required documentation:
 - Protocol with all amendments
 - The Skin Test IFU (Appendix 3) and Bellafill IFU (Appendix 4)
 - Copies of all pre-study documentation and all correspondence to and from the IRB and the Sponsor or Sponsor representatives
 - An up-to-date curriculum vitae for the principal Investigator.
 - Signed and dated Investigator agreement
 - Copies of all written communications with the IRB including all approval forms.
 - A copy of the IRB approved informed consent form and other adjunctive materials (e.g., advertising) used in the study, including written documentation of IRB approval of these items.
 - In addition to the documents required prior to the study, other documentation may be required during the course of the study.

13.4.1 Source Documents

Individual subject records will be maintained in the Investigator's Source Documents (SDs). Source documentation is generally considered to be the document on which the information or data point was first recorded. SDs may include source document worksheets, a subject's medical records, hospital charts, clinic charts, and the Investigator's study files as well as the results of diagnostic tests such as X-rays, laboratory tests, and electrocardiograms.

13.4.2 Electronic Case Report Form (eCRF) Completion

Treatment and follow-up of subjects will be recorded in a 21 CFR part 11 compliant eCRF. Data will be first recorded into the medical record and study specific source document worksheets, as applicable, prior to entry into the eCRF.

The study coordinator will refer to the source document worksheets in conjunction with the medical record in order to complete data entry into the eCRF.

In order to review and electronically sign the eCRF, the Investigator will have individual login passwords that will allow them to entered data. The Investigator must ensure that they electronically sign for completed eCRFs on a timely basis.

